10.5.2 Other secondary efficacy objectives

The following intracranial, extracranial and whole body (for lesions **in and outside** the brain) tumor-response related endpoints (OIRR, IDCRC, TTIR, DOIR, OERR, EDCR, TTER, DOER, TTR, DOR and PFS) will be assessed separately based on investigator assessment and BIRC assessment per RECIST 1.1.

All the endpoints described below will be summarized by prior radiotherapy to the brain (yes, no), prior ALK inhibitor use (yes, no) and overall using the data from Arms 1 through 4. Secondary efficacy endpoints will also be summarized using data from Arm 5 separately.

[REDACTED]

Intracranial endpoints:

Overall intracranial response rate (OIRR): OIRR is calculated based on response assessments in the brain for patients having measurable brain metastases at baseline. The OIRR is defined as the proportion of patients with a best overall confirmed response of CR or PR in the brain as assessed per modified RECIST 1.1. OIRR will be estimated and the exact binomial 95% CI will be presented.

Intracranial disease control rate (IDCR) at 8 and 16 weeks and overall: IDCR is calculated based on response assessments in the brain for patients having evaluable (measurable or non-measurable) brain metastases at baseline. In what follows, CR, PR and SD are possible responses only for patients with measurable brain metastases at baseline, while non-CR/non-PD is a possible response only for patients without measurable brain metastases at baseline.

- The IDCR at 8 and 16 weeks is defined as the proportion of patients with CR, PR, SD or non-CR/non-PD assessment in the brain at Week 8 and Week 16 intracranial tumor evaluations respectively.
- IDCR overall is defined as the proportion of patients with a best overall response of CR, PR, SD or non-CR/non-PD in the brain, as assessed per modified RECIST 1.1 by the investigator.
IDCR will be estimated and the exact binomial 95% CI will be presented.

Time to intracranial tumor response (TTIR): TTIR is defined as the time from the date of the first dose of ceritinib to the date of the first documented response (CR or PR) in the brain as assessed per modified RECIST 1.1 criteria for patients with measurable brain metastases at baseline.

The distribution function of TTIR will be estimated using the Kaplan-Meier method. The median TTIR along with 95% CI will be presented.

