Duration of intracranial response (DOIR): Among patients with measurable brain metastases at baseline and a confirmed response (PR or CR) in the brain per modified RECIST 1.1, DOIR is defined as the time from the first documented response (PR or CR) in the brain to the date of the first documented disease progression in the brain or death due to any cause. The distribution function of DOIR will be estimated using the Kaplan-Meier method. The median DOIR along with 95% CI will be presented.

Extracranial endpoints:

Overall extracranial response rate (OERR): OERR is defined as the proportion of patients with a best overall confirmed response of CR or PR outside of the brain, as assessed per RECIST 1.1. OERR will be estimated and the exact binomial 95% CI will be presented.

Extracranial disease control rate (EDCR) at 8 and 16 weeks and overall:

- EDCR at 8 and 16 weeks is defined as the proportion of patients with CR, PR or SD outside of the brain at Week 8 and Week 16 extracranial tumor evaluations respectively, as assessed per RECIST 1.1.
- EDCR overall is defined as the proportion of patients with a best overall response of CR, PR or SD outside of the brain as assessed per RECIST 1.1.

EDCR will be estimated and the exact binomial 95% CI will be presented.

Time to extracranial tumor response (TTER): TTER is defined as the time from the date of the first dose of ceritinib to the date of the first documented response (CR or PR) outside of the brain as assessed per RECIST 1.1 criteria. The distribution function of TTER will be estimated using the Kaplan-Meier method. The median TTER along with 95% CI will be presented.

Duration of extracranial response (DOER): Among patients with a confirmed response (PR or CR) outside of the brain per RECIST 1.1, DOER is defined as the time from the first documented response (PR or CR) outside of the brain to the date of the first documented disease progression outside of the brain or death due to any cause. The distribution function of DOER will be estimated using the Kaplan-Meier method. The median DOER along with 95% CI will be presented.

Whole body endpoints:

ORR by BIRC: The evaluation of ORR will be repeated based on BIRC assessment.

DCR by BIRC: The evaluation of DCR will be repeated based on BIRC assessment.

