Time to tumor response (TTR): TTR is defined as the time from the date of the first dose of ceritinib to the date of the first documented response (CR or PR) in the whole body as assessed per RECIST 1.1 criteria. The distribution function of TTR will be estimated using the Kaplan-Meier method. The median TTR along with 95% CI will be presented.

Duration of response (DOR): Among patients with a confirmed response (PR or CR) in the whole body per RECIST 1.1, DOR is defined as the time from the first documented response (PR or CR) to the date of the first documented disease progression or death due to any cause. The distribution function of DOR will be estimated using Kaplan-Meier method. The median DOR along with 95% CI will be presented.

Progression-free survival (PFS): PFS is defined as the time from the date of the first dose of ceritinib to the date of the first documented disease progression in the whole body per RECIST 1.1 or death due to any cause. A patient who has not progressed or died at the date of the analysis or when he/she receives any further anticancer therapy in the absence of disease progression will be censored at the time of the last adequate tumor evaluation before the earlier of the cut-off date or the anticancer therapy date. By default, if disease progression or death for any reason is documented after one single missing tumor evaluation, the actual event date of disease progression/death will be used for the PFS event date. If disease progression or death for any reason is documented after two or more missing tumor evaluations, the PFS time of these patients will be censored at the date of the last adequate tumor evaluation without PD. The distribution of PFS will be estimated using the Kaplan-Meier method. The median PFS along with 95% CI will be presented.

Overall survival (OS): OS time is defined as time from the date of first dose of ceritinib to the date of death due to any cause. OS time for patients who are alive at the end of the study or are lost to follow-up will be censored at the date of last contact. OS will be estimated using the Kaplan-Meier method. The median OS along with 95% CI will be presented. Kaplan-

Meier curves will not be produced for Arm 5 alone if the number of patients enrolled in this arm is ≤ 10 .

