14.2.24 Time to response

Time to overall response (CR or PR) is the time between date of randomization/start of treatment until first documented response (CR or PR). The response may need to be confirmed depending on the type of study and its importance. Where the response needs to be confirmed then time to response is the time to the first CR or PR observed.

Although an analysis on the full population is preferred a descriptive analysis may be performed on the “responders” subset only, in which case the results should be interpreted with caution and in the context of the overall response rates, since the same kind of selection bias may be introduced as described for duration of response in [Section 14.2.23](#). It is recommended that an analysis of all patients (both responders and non-responders) be performed whether or not a “responders only” descriptive analysis is presented. Where an inferential statistical comparison is required, then all patients should definitely be included in the analysis to ensure the statistical test is valid. For analysis including all patients, patients who did not achieve a response (which may have to be a confirmed response) will be censored using one of the following options.

- at maximum follow-up (i.e. FPFV to LPLV used for the analysis) for patients who had a PFS event (i.e. progressed or died due to any cause). In this case the PFS event is the worst possible outcome as it means the patient cannot subsequently respond. Since the statistical analysis usually makes use of the ranking of times to response it is sufficient to assign the worst possible censoring time which could be observed in the study which is equal to the maximum follow-up time (i.e. time from FPFV to LPLV)
- at last adequate tumor assessment date otherwise. In this case patients have not yet progressed so they theoretically still have a chance of responding

Time to overall complete response (CR) is the time between dates of randomization/start of treatment until first documented CR. Similar analysis considerations including (if appropriate) censoring rules apply for this endpoint described for the time to overall response endpoint.

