#### 2.8.1.2.3 Whole body endpoints

**ORR by BIRC:** The evaluation of ORR will be repeated based on BIRC assessment by study arm and for all patients. Additionally, ORR by BIRC will also be presented by prior radiotherapy to the brain (yes, no) and prior ALK inhibitor use (yes, no) and overall using the data from Arms 1 through 4.

**DCR by BIRC:** The evaluation of DCR will be repeated based on BIRC assessment by study arm and for all patients. Additionally, DCR by BIRC will also be presented by prior radiotherapy to the brain (yes, no) and prior ALK inhibitor use (yes, no) and overall using the data from Arms 1 through 4.

**Time to tumor response (TTR):** TTR is defined as the time from the date of the first dose of ceritinib to the date of the first documented response (CR or PR) in the whole body as assessed per RECIST 1.1 criteria.

TTR will be summarized by frequency counts in time intervals and using descriptive statistics for patients with confirmed CR or PR.

These analyses of TTR will be performed separately based on investigator assessment and based on BIRC assessment.

**Duration of response (DOR):** Among patients with a confirmed response (PR or CR) in the whole body per RECIST 1.1, DOR is defined as the time from the first documented response (PR or CR) to the date of the first documented disease progression or death due to any cause.

DOR will be described by study arm and for all patients using Kaplan-Meier methods, including estimated median (in months) with 95% CI, 25th and 75th percentiles and Kaplan-Meier estimated probabilities with corresponding 95% CIs at pre-specified time points.

Additionally, DOR will also be presented by prior radiotherapy to the brain (yes, no) and prior ALK inhibitor use (yes, no) and overall using the data from Arms 1 through 4.

These analyses of DOR will be performed separately based on investigator assessment and based on BIRC assessment.

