**Table 3-1 Changes to protocol specified analysis or descriptions and rationale**

Protocol Section	Protocol Description	Change
Section 10.5.2	The distribution function of TTIR will be estimated using the Kaplan-Meier method. The median TTIR along with 95% CI will be presented. TTIR will be summarized by prior radiotherapy to the brain (yes, no), prior ALK inhibitor use (yes, no) and overall using the data from Arms 1 through 4. Similar for TTER and TTR.	TTIR will be summarized by frequency counts in time intervals and using descriptive statistics for patients with confirmed CR or PR. This analysis is removed. This update was made because median value is not estimable using KM method due to low response rate. Descriptive statistics suggested median

---

		values were consistent across study arms.
Section 10.5.2	A patient who has not progressed or died at the date of the analysis or when he/she receives any further anticancer therapy in the absence of disease progression will be censored at the time of the last adequate tumor evaluation before the earlier of the cut-off date or the anticancer therapy date.	A patient who has not progressed or died at the date of the analysis cut-off will be censored at the time of the last adequate tumor evaluation performed on or before the cut-off date. This update was made to align with the latest “Guidelines for response, duration of overall response, TTF, TTP, progression-free survival, and overall survival”.

---

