#### 4.6.4 Kaplan-Meier estimates

To analyze time to event variables (DOIR, TTIR, DOER, TTER, DOR, TTR, OS and PFS) an estimate of the survival function will be constructed using **Kaplan-Meier (product-limit) method** as implemented in SAS PROC LIFETEST with METHOD=KM option (see example below). The TIME statement will include a variable with survival times (*survtime* in the example below) and a (right) censoring variable (*censor* in the example below) with a value of 1, representing censoring:

```
PROC LIFETEST data = dataset  
    METHOD = KM  
    CONFTYPE=LOGLOG;  
TIME survtime*censor(1);  
RUN;
```

/\* *survtime* represents variable containing event/censor times;  
*censor* represents censoring variable (1 = censored, 0 = event); \*/

Kaplan-Meier survival and failure function estimates from this procedure will be used to construct the Kaplan-Meier figures.

Median survival will be obtained along with 2-sided 95% CIs calculated from PROC LIFETEST output using the method of [Brookmeyer & Crowley, 1982](#).

Kaplan-Meier estimates with 2-sided 95% CIs at specific time points will be summarized. The time points can be expressed in weeks or in months depending on the time-to-event variable. The CIs will be constructed using Greenwood's formula [Collet, 1994, p.23] for the standard error of the Kaplan-Meier estimate.

The PROC LIFETEST statement will use the option CONFTYPE=LOGLOG. The CONFTYPE option specifies the transformation applied to the survival function to obtain the point-wise confidence intervals and the confidence intervals for the quartiles of the survival times. The LOGLOG keyword specifies the complementary log-log transformation (Collett, 1994; Lachin, 2000)  $g(x)=\log(-\log(x))$  which ensures that the point-wise confidence intervals are always within interval [0,1]. Although the LOGLOG is the default option in SAS v 9.4, it should be explicitly shown.

The Kaplan-Meier graphs will be constructed using SAS software.

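### The SAP replaces the protocol's Kaplan-Meier analysis of time to response with a responders-only description, gives results as the reason, and still lists the same endpoints for Kaplan-Meier

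*SAP*

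**What the plan says.** Protocol 10.5.2 gives the same method for all three endpoints. For the intracranial one: "The distribution function of TTIR will be estimated using the Kaplan-Meier method". For the extracranial one: "The distribution function of TTER will be estimated using the Kaplan-Meier method". For the whole body: "The distribution function of TTR will be estimated using the Kaplan-Meier method". Each is to be reported as a median with a 95% CI. None is restricted to responders. TTIR is limited to patients with measurable brain metastases at baseline.

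Protocol Appendix 2, section 14.2.24, says: "It is recommended that an analysis of all patients (both responders and non-responders) be performed". This applies whether or not a responders-only description is also shown. The section gives censoring options for patients who never respond: maximum follow-up if they had a PFS event, otherwise the last adequate tumor assessment.

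SAP 2.8.1.2 changes the method. For the whole body: "TTR will be summarized by frequency counts in time intervals and using descriptive statistics for patients with confirmed CR or PR". TTIR and TTER are treated the same way. Table 3-1 declares the change and gives two reasons. The first is "This update was made because median value is not estimable using KM method due to low response rate". The second is that descriptive statistics had pointed to consistent medians across arms.

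SAP 4.6.4, on Kaplan-Meier estimation, begins "To analyze time to event variables (DOIR, TTIR, DOER, TTER, DOR, TTR, OS and PFS" and goes on to specify PROC LIFETEST for that list.

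**The concern.** There are three difficulties.

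- **The reason does not support the change.** If fewer than half of patients respond, the all-patient median is not reached, and that is the correct report. The curve and the response probabilities at fixed weeks remain estimable.
- **The reason rests on results.** Both parts of the Table 3-1 rationale describe observed response, and the table does not say which data were looked at.
- **The SAP is not consistent with itself.** One section calls for a descriptive summary in responders. Another lists the same endpoints for a survival-curve procedure, with no censoring rule to run it on all patients.

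A time to response computed only in responders conditions on a later outcome. It describes how quickly responders responded, not how quickly treated patients came into response. A reader who takes it for the latter would be misled, and two programmers could produce different tables.

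**Working it through.** **1. Did the protocol mean all patients?** Section 10.5.2 does not use that phrase, so this is an inference from three places.

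- Where the protocol wants responders only, it says so: "Among patients with a confirmed response (PR or CR) in the whole body per RECIST 1.1, DOR is defined as". TTIR, TTER and TTR carry no such clause.
- Protocol 10.1.1 makes the FAS (all treated patients) the default efficacy set.
- Section 14.2.24 recommends the all-patient analysis and supplies its censoring.

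SAP Table 2-1 does not settle the matter. It lists the FAS for TTR, but also for DOR, which is confined to responders by definition.

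**2. The plan's own planning figure.** SAP Table 2-4 gives 70/140 = 50% with exact 95% CI (41.44%, 58.56%). The Clopper-Pearson limits are the 2.5% quantile of Beta(70, 71) and the 97.5% quantile of Beta(71, 70). These give 41.44% and 58.56%, so the figure reproduces. All 22 rows of Tables 2-4 and 2-6 reproduce to within 0.01 percentage point.

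**3. Does a non-estimable median follow from the planning rates?** Under the 14.2.24 censoring, non-responders who progress or die stay in the risk set to maximum follow-up. The curve therefore levels off near the response rate, and the median is reached when about half or more respond. With X ~ Binomial(n, p), P(X ≥ n/2) = Σ C(n,k) p^k (1−p)^(n−k), summed over k from n/2 to n. The true rates are assumptions shown as a range.

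| True rate | n = 140 (Arms 1-4) | n = 70 (measurable brain metastases) |
|---|---|---|
| 40% | 0.010 | 0.057 |
| 45% | 0.135 | 0.235 |
| 50% | 0.534 | 0.548 |
| 55% | 0.898 | 0.832 |
| 60% | 0.993 | 0.965 |

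Table 2-4 plans on an ORR of 50% to 60% in 140 patients, which gives 0.53 to 0.99. Table 2-6 plans on an OIRR of 45% to 60% in 70, which gives 0.24 to 0.97. So the reason in Table 3-1 is not a consequence of the design; it is a statement about what was observed.

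**4. What the responders-only median measures.** With response rate R, the share of all patients who have responded by that median is 0.5 × R. That is 20% at R = 40% and 30% at R = 60%.

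Let f be the share of responders whose response is first seen at the week-8 scan. The responders-only median depends on the timing among responders, and not on R. The share of all patients in response by that scan is f × R. The values of f and R below are assumptions.

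| f | Responders-only median | R = 35% | R = 70% |
|---|---|---|---|
| 80% | about week 8 | 0.80 × 0.35 = 28% | 0.80 × 0.70 = 56% |
| 60% | about week 8 | 0.60 × 0.35 = 21% | 0.60 × 0.70 = 42% |
| 40% | a later scan | 0.40 × 0.35 = 14% | 0.40 × 0.70 = 28% |

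Protocol 1.2.1.2.2 shows the same insensitivity in earlier ceritinib data. The median time to response was 6.1 weeks both with a prior ALK inhibitor (ORR 54.6%) and without (ORR 66.3%), although the rates differ by 66.3 − 54.6 = 11.7 points. Similar medians across arms are thus weak evidence for preferring the responders-only method.

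**5. SAP sections side by side.**

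- 2.8.1.2: descriptive statistics in confirmed responders for TTIR, TTER and TTR.
- 4.6.4: the same three endpoints listed for Kaplan-Meier, with no population named.
- Table 2-2: event and censoring rules for DOIR, DOER, DOR and PFS only.
- Table 3-1: against the protocol's summary by prior radiotherapy and prior ALK inhibitor, it says the analysis is removed. SAP 2.1 and the Table 2-1 footnote still present efficacy endpoints by those groups.

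**The case against.** The case for leaving the SAP largely as it stands has weight.

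- Section 14.2.24 expressly allows a descriptive analysis in responders, read with caution. It insists on all patients only where an inferential comparison is needed, and SAP 2.7.2 says no hypothesis is tested. This stands: the SAP departs from the method in 10.5.2 and from a recommendation in the appendix, but a responders-only description is not itself prohibited.
- Little information is lost. ORR, OIRR and OERR are reported with exact intervals, and interval counts divided by N give most of the cumulative response. This largely stands, although the reader has to do the division and no interval estimate comes with it.
- The 4.6.4 list looks like a leftover. SAP section 4 describes itself as implementing section 2, and Kaplan-Meier on uncensored responders is simply the empirical distribution. This lowers the importance of the conflict but does not remove it.
- The protocol's own background reports time to response among the 144 confirmed responders. That is a precedent for showing such a summary, not for dropping the other.

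Two stronger readings are tempting. One is that the responders-only median must sit near 8 weeks whatever the drug does. That holds only if more than half of responders first respond at the first scan; otherwise it moves to a later one. The other is that the method was changed after the final data had been seen. SAP section 1 states that decisions preceded database lock, and the change is declared. The trial is open-label and Protocol 4.3 allows an early analysis of some arms, so results could have been seen before lock. The documents do not say which data were used.

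**Conclusion.** The point holds in limited form. The SAP drops an analysis that the protocol specifies and its appendix recommends. Its reasons describe results and do not require the change, and 4.6.4 is left at odds with 2.8.1.2. The consequence is modest: these are secondary, descriptive endpoints, no type I error is involved, and the change is disclosed. What suffers is the interpretation of time to response, the independence of the method from the data, and the certainty of what will be programmed.

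The conclusion rests on reading 10.5.2 as covering all patients in the relevant set, which is well supported but inferred. The probabilities in the check rest on assumed true response rates. The documents give no observed rate for this trial, so they cannot show how low the response was or whether the median would in fact be unreached.

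**What to change.** 1. In SAP 2.8.1.2, keep an all-patient Kaplan-Meier analysis of TTER and TTR in the FAS, and of TTIR in patients with measurable brain metastases at baseline. Report cumulative response at about weeks 8, 16 and 24. Since imaging may be up to 7 days late, reading the curve at the close of each window (weeks 9, 17 and 25) avoids missing on-schedule responses.
2. Present the responders-only summary beside it, labelled as such.
3. Add the 14.2.24 censoring to Table 2-2 or a companion table: maximum follow-up for non-responders with a PFS event, last adequate assessment for the rest. State whether, for TTIR and TTER, that event means progression in the compartment or in the whole body.
4. Make 2.8.1.2, Table 2-2, Table 3-1 and 4.6.4 agree, including whether the summaries by prior radiotherapy and prior ALK inhibitor are kept. If the sponsor retains only the responders-only description, the minimum is to delete TTIR, TTER and TTR from 4.6.4.
5. In Table 3-1, state which data prompted the change and when they were seen.

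The cost is SAP wording and one extra table per endpoint. Some medians may have to be reported as not reached. No new data are needed.
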